Proposed time period for retention of relevant trial documentation: All hard copies of the trial data will be kept in a locked room in a locked cabinet at UEA in the Norwich Medical School or at participating NHS sites for the period of the trial and for a balance of ten years. All of this information will be coded and kept separate from the identifying information. Thereafter, it will be destroyed using the confidential shredding and recycling facility made available for the disposal of all confidential written material at the university or participating NHS sites.

7. Proposed sample size: Our intention for the pilot study is therefore to recruit 100 participants, 50 treated cases and 50 controls. This will allow the assessment of recruitment and feasibility of intervention across this age range together with an assessment of variability in outcome for a future power calculation. The qualitative study will be carried out with 16 participants (8 from each group) who will be selected using a sampling frame, drawn to sample purposefully for key constituencies, such as age, presentation, symptoms and previous history.

If it is decided to proceed to substantive trial using the present study as an internal feasibility stage we will present a full power calculation in a future bid to HTA at month 18. This will include data on mean and SD of our primary and secondary outcome from the proposed pilot study. Our previous studies suggest the likely mean activity of the target population will be approximately 12 hours (with an estimated SD 9). Given a minimum clinically significant benefit is an increase of 4 hours activity and a conservative estimate of effect in the 0.3 to 0.4 range our current estimate would be that a trial with a sample size of approximately 300 cases would have sufficient power to provide a definitive test in a substantive trial. On this basis if it is decided to use the present study as an internal feasibility phase it is placed to be able to recruit between a third and a half of the participants required in a substantive trial. If not it can make a significant contribution to suggesting effect size as a significant external pilot study.

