8. Statistical analysis of outcome: The main aim of the pilot project is to undertake feasibility studies. The criteria for the first phase are therefore the ability to successfully recruit a sample of suitable cases. Analysis of baseline data of the first phase aims to describe the mean and SD of the primary and secondary outcome measures to prepare a definitive sample size calculation.

If it is decided to set aside the results and publish them as an external pilot, the main analyses will use general linear models with the inclusion of treatment group and stratification baseline variables. The outcome variables will be checked for distributional assumptions (i.e. following a Normal distribution) and transformation will be applied if necessary,

For both the primary and secondary outcomes we will check the extent and patterns of missing data and use multiple imputation if it is felt necessary. Factors to include in the imputation model will be those that are likely to be related to the outcomes (a clinical decision) and those related to missingness (a statistical decision). The analysis using imputed data will be a secondary, sensitivity, analysis with complete case analysis being the primary analysis.

9. Economic evaluation: The estimation of cost-effectiveness, within a health technology assessment, is an iterative process (Ramsey et al, 2001). Here we aim to monitor levels of resource use and quality of life, with a view to inform the decision as to how costs and benefits would be measured as part of any future more definitive study. A preliminary within trial cost-effectiveness analysis of multisystemic social recovery CBT compared to treatment as usual will also be undertaken. In line with guidance by the National Institute of Health and Clinical Excellence (NICE, 2008) costs will be calculated from the perspective of the NHS and personal social services (PSS). A modified version of the Client Service Receipt Inventory (Thornicroft et al, 2006) will be used to monitor levels of resource use associated with both interventions (including intervention staff training and supervision, along with all visit related costs) and other NHS and PSS resource items, such as hospital admissions/visits, which may relate to the interventions in question. Appropriate unit costs (e.g. Curtis et al, 2009) will subsequently be attached to all items of resource use.

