Prior to start of the study: Preparations to be made before the beginning of the study will be a) obtaining ethics and research governance approvals (b) publicising the study to senior managers, clinicians and service users in the sites participating in the study (c) recruiting the first three members of staff beginning with the trial manager who will participate in the recruitment of other staff. (d) trial therapists will be identified before the start of the study and attend a series of pre study workshops discussing client information and undertaking their own pilot cases using the therapy manual.

The first 3 months (study set up period): The study will begin when the senior RAs are recruited in each centre. The process of publicising the study will continue. Therapy procedures and the procedures for optimal

treatment as usual will be finalised. Training will be provided for therapists in delivering the intervention. Training will be provided for the RAs in undertaking assessments.

Pilot study recruitment (Months 4 to 9): In month 4 recruitment to the pilot study will begin in teams in Norfolk and Manchester. Randomisation will follow gaining informed consent and an initial interview. Recruitment will continue for 6 months and patients will be followed up initially at 3 months.

Pilot study follow up assessments (months 7 to 12): Participants in the pilot study will initially be assessed at 3 months. At this point we will assess the feasibility of proceeding to a full trial, based on recruitment at this period. Pilot study follow up assessments will end in month 12(?15). Qualitative interviews will be undertaken at baseline and at three months.

Decision making and preliminary pilot study write up: (months 12 to 18): In months 13 and 14 we will consult the DMC as described above in order to decide whether to regard the data collected as an internal pilot and proceed to a full trial application or to set aside the data and change the protocol and write the preliminary pilot phase up as an external pilot. We will present to the HTA data on recruitment and retention in the pilot phase in order to obtain ratification of the decision and if necessary guidance. If the decision is not to proceed to a full trial we will make alterations to the inclusion criteria and changes to the protocol suggested by the preliminary pilot phase and continue recruiting to the study from the above 3 month stage reviewing again in between months 24 and 30.

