At months 24 to 30: there will either be a repeat of the decision making and preliminary pilot stage as above for the second phase pilot. Or a decision will have been made to continue with data collection as the internal pilot for a substantive trial in which case a submission to HTA for a fast track full trial will be made at 18 months with data continuing in the present study till month 30 which will allow time for the team to continue with the project until a decision on funding is made.

At month 30: the project data collection will finish and depending on the decisions of the above committees according to the qualitative and quantitative data. The data will either be written up as a substantive pilot project involving 100 cases, as a series of external pilots of 40 and 60 cases respectively or it will be the first phase of a larger trial which will continue with another centre depending on power calculation.

14. Team expertise: This project draws together a team of investigators who have considerable experience in designing, running and utilising complex pilot studies of this type. The applicants have considerable experience of working together on previous projects and have established track records in engaging young people in research, and developing innovative psychological interventions.

15. Service Users: We have consulted service users in the course both of preparation of the outline and the full proposal, and we are also planning considerable input to the main study. In the course of preparing the outline and full proposal, we consulted service users in the Norfolk Early Intervention Service regarding the study, focusing especially on the feasibility and acceptability of the intervention and how best to implement it. The main topics in our consultation, which has informed preparation of the proposal and decisions about the intervention, have been the content, presentation and acceptability of the intervention, best methods for recruiting to the trial, and the best way of engaging service users in the research process.

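### On the internal-pilot route the power calculation is due at month 18, when about 40 of the 100 participants can have a 9-month outcome and none a usable 15-month outcome; Section 8 would take the SD from baseline hours that are cut off at entry

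*Protocol*

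**What the plan says.** Section 7 sets the pilot size: "recruit 100 participants, 50 treated cases and 50 controls". It gives recruitment and feasibility as reasons, "together with an assessment of variability in outcome for a future power calculation".

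The next paragraph of Section 7 covers the internal-pilot route: "we will present a full power calculation in a future bid to HTA at month 18". Of that calculation it says: "This will include data on mean and SD of our primary and secondary outcome from the proposed pilot study". Section 13 repeats the date: "a submission to HTA for a fast track full trial will be made at 18 months". Appendix a also has the application going in by month 18, and mentions recruitment and retention data as its content.

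Section 8 names a different source for the SD: "Analysis of baseline data of the first phase aims to describe the mean and SD of the primary and secondary outcome measures". It says that this is to prepare the definitive sample size calculation.

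On timing, Section 13 says: "In month 4 recruitment to the pilot study will begin in teams in Norfolk and Manchester". It continues: "Recruitment will continue for 6 months and patients will be followed up initially at 3 months". Section 3 gives each participant a 9-month intervention and six further months of follow-up, and Section 10 lists assessments at baseline, 9 and 15 months.

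**The concern.** Section 7 ties the assessment of outcome variability to 100 participants, but dates the calculation that uses it to a point when most of those outcomes cannot yet exist. Section 8 avoids the timing problem only by using a different quantity, the spread of hours at baseline. Entry requires fewer than 30 hours per week on essentially the variable used as primary outcome, so the baseline SD comes from a distribution cut off at 30. Nothing cuts off the follow-up distribution, and the therapy aims to move people up it.

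The month-18 bid would set the size of the definitive trial. An SD that is low by chance (few participants) or by construction (truncated baseline) would make that trial too small.

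**Working it through.** **Inputs.** Recruitment starts at the beginning of month 4, that is, after 3 elapsed months (Section 13). Accrual is 3 to 4 per month in each of two sites, so 6 to 8 per month, over 15 months (Section 3). Outcomes fall at 9 and 15 months. Primary-outcome retention is taken at the 90% progression criterion (Section 1). The bid is at month 18.

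**The plan's own figures.**
- 15 months × 6 to 8 = 90 to 120, which brackets the 100.
- On plan, 100/15 = 6.67 per month, and 6.67 × 6 months = 40. This matches the year-1 milestone of at least 40 in Appendix a.

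**Outcomes available by the end of month 18.** Number = monthly accrual × max(0, 18 − T − 3), where T is the follow-up time in months.
- T = 9: window of 6 months. 6.67 × 6 = 40 on plan; 6 × 6 = 36 to 8 × 6 = 48 over the stated rates. At 90% retention: 36 on plan, range 32 to 43.
- T = 15: window of 0 months. Someone randomised at the very start of month 4 reaches 15 months only as month 18 ends.
- If the data must be ready by the end of month 17, the 9-month count falls to 33 (30 to 40) before attrition.

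**Precision of the SD.** 95% limits for true SD / estimated SD = √(df/χ²), with df = n − 2.

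| n | lower | upper |
|---|---|---|
| 36 | 0.81 | 1.31 |
| 40 | 0.82 | 1.29 |
| 48 | 0.83 | 1.26 |
| 90 | 0.87 | 1.17 |
| 100 | 0.88 | 1.16 |

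To show the scale, take Section 7's 4-hour difference and SD of 9. Assume a two-sided 5% level and 90% power (the protocol states neither). Total N = 4(1.960 + 1.282)² × 9²/4² ≈ 213, or 214 with whole participants per arm. Putting the limits in for the SD gives 140 to 366 with 36 participants and 162 to 294 with 90.

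**The baseline alternative in Section 8.** By month 18, baseline data would exist for about 40 + 6 × 60/18 = 60 participants at the Appendix a pace, and up to 100 at the Section 3 pace. The number is therefore larger, but the distribution is truncated. Appendix b gives an SD of 8.71 hours for EDIE 2 cases below 30 hours. Its Table 1 gives SDs for structured activity of 27.81 in the EDIE sample and 17.54 in ISREP. For a 4-hour difference (two-sided 5% and 80% power assumed), total N is 150 at SD 8.71 and 604 at SD 17.54. This pair is illustrative: the other samples are not follow-up data on a group selected below 30 hours, and this trial's follow-up SD is unknown.

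**The case against.** The strongest reply is that Section 8 names the source of the SD, and it is baseline, so a shortage of 9-month outcomes does not describe the written plan. That stands as a reading of Section 8. It does not settle the matter, because Section 7 speaks of variability in outcome and because baseline hours are truncated by the entry rule. The 3-month assessment in Section 13 does not help either: it falls inside the 9-month intervention.

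Four stronger readings are tempting, and the protocol does not support them.
- A reader might infer that the 100 rest on SD estimation alone. Section 7 lists recruitment and feasibility first, and the external-pilot route would use all 100.
- A reader might take 40 as a ceiling. It is the planned figure; the stated rates allow up to 48 randomised, or 43 retained.
- A reader might infer that the bid will ignore the imprecision of the SD. The bid is a future document that is not shown. Section 7 says that it will include pilot data, not that it will rely on them alone. The current planning already has some margin: 4 hours at SD 9 is a standardised effect of 0.44, while Section 7 plans on 0.3 to 0.4, which for 4 hours implies an SD of 10 to 13.3.
- A reader might rescale the approximate 300 for the full trial by the SD limits. Section 7 reaches 300 from the standardised effect range, not from an SD, so that rescaling has no basis.

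**Conclusion.** The point holds as a conflict between the stated basis and the stated date. On the internal-pilot route the outcome SD available at month 18 rests on about 40 participants at 9 months (36 to 48 randomised, 32 to 43 at 90% retention) and on none at 15 months. With 36, the SD is known to within 0.81 to 1.31 times its estimate, against 0.87 to 1.17 with 90. The baseline SD in Section 8 is not a sound substitute and may be too low; by how much cannot be told from the protocol.

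This assumes recruitment at the stated rates from the start of month 4, a bid at the end of month 18, and roughly Normal outcomes for the chi-square limits. Slower recruitment or an earlier data cut makes the number smaller. The external-pilot route is not affected by the month-18 date.

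**What to change.** Reconcile Sections 7, 8 and 13 so that they name one source for the month-18 SD.
- State that on the internal-pilot route it comes from the 9-month outcome, pooled over arms without unblinding, in about 32 to 43 participants, with none at 15 months.
- State that the truncated baseline hours are not used for this purpose.
- Report the SD in the bid with its confidence interval.
- Commit to a blinded update of the SD and sample size once all pilot participants have reached 9 months. On Section 3's schedule that is month 3 + 15 + 9 = 27. At the Appendix a pace (60 more over the 18 months after month 12) it is month 12 + 18 + 9 = 39, beyond the month-30 end of data collection, so the protocol should say which schedule applies.

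The cost is wording and a little analysis; recruitment, treatment and assessments do not change. The first N in the bid will be less precise than one from 100 participants, and may be revised. A blinded SD also absorbs any treatment difference, but only slightly: with SD 9 and a 4-hour difference it becomes √(81 + 4²/4) = √85 = 9.22.

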Our analyses suggest that a useful cut off for isolating a socially disabled group using the Time use Assessment may be performing at a level of less than 30 hours per week total structured activity. As can be seen above this is less than half the mean level of functioning of young people in the normal population. Analyses of the EDIE 2 trial data and referral patterns to our existing clinical services suggest that this is a population of young people who have severe and complex needs which are not met by current interventions, but are a group which are help seeking and already being referred into research trials and clinical services (though often at present excluded). Several recent national reports have highlighted the unmet needs of this population (Singh et al, 2010; DoH, 2008) and our research and clinical experience has already shown we can recruit samples into studies. Our analyses of the MRC EDIE 2 trial data showed that 122/205 (60%) cases in EDIE were functioning at this level with structured activity below 30hrs per week. This subgroup are engaged at a very low level of activity (mean less than 15 hours total structured activity in a week) and they are a more homogeneous sample (Mean 13.96 SD = 8.71). Our established clinical services for detection of cases at risk of psychosis which we successfully used in the completion of the EDIE 2 multicentre trial can therefore provide a large source of the referrals for this study. In addition we also intend to recruit young people who have severe and complex mental health problems and social impairment but who have less severe attenuated psychotic symptoms (and thus were excluded from EDIE 2 and early intervention services as they do not meet symptomatic criteria for an At Risk Mental state or Psychosis). We get many referrals to our existing clinical services of this type. In Norfolk we ran a pilot service for young people aged 14 to 18 which included this group. This clinical pilot has been highlighted as an example of clinical excellence in engaging and treating young people (Joint working at the interface, 2011) and shown that such cases are available for recruitment as they are commonly referred to early detection and intervention services for psychosis (though currently excluded). Also this group includes young people with severe and complex mental health problems who are not in education, employment and training (NEET) who are identified as being at high risk by statutory agencies and are therefore a priority group to target. The group has a similar levels of time use to that of the EDIE 2 sample (mean less than 15 hours, SD 9).

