
In summary, the Time Use Survey is a well known and validated instrument. We have shown it is acceptable, reliable, and sensitive to change and thus highly suitable to be used as the primary outcome to assess social functioning levels in a randomised controlled trial involving young people with severe and complex mental health problems and social impairment.

	Constructive Economic	Structured
		(without hobbies)
EDIE Young people with Ultra high risk symptoms (N = 288)	25.11 (27.05)	30.67 (27.81)
EDEN Young people with first episode psychosis (N = 1027)	17.23 (23.80)	25.44 (27.10)
ISREP Young people with chronic psychotic disorder and social impairment	12.43 (17.05)	19.66 (17.54)
(N = 77)		
ONS Aged matched young people in the normal population (N = 6000)	50.93 (25.40)	64.18 (27.22)

Table 1. Comparison of Constructive Economic and Structured Time Use across studies – Mean hours per week (SD)

Note. Constructive Economic Activity = work, education, voluntary work, childcare & chores

Structured Activity = Constructive Economic Activity plus leisure and sports activities

c. Further detail regarding the proposed qualitative study

The proposed methods for collecting qualitative data from young people draw on earlier studies of young people's experiences of mental health services and participating in research. These studies have highlighted the importance of flexible data collection processes; of researchers being skilled in engaging with and working at the pace of young people often presenting with multiple difficulties and complex care histories (Street & Svanberg 2003), of the ethical implications of researching vulnerable young people (Taylor et al 2010), and of being able to work across and gather information from a range of different agencies (Garcia, Vasiliou & Penketh 2007). Studies have suggested the importance of service user involvement in understanding the views of those with emergent signs of severe mental illness (Hardy, Dickson, & Morrison, 2009) and in this study, we intend to involve service users at all project stages as much as possible.

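### Section 8 takes the SD for the definitive sample size from baseline hours, which the under-30 h entry rule compresses, while Section 7 promises variability in outcome

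*Protocol*

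**What the plan says.** Section 8 (Statistical analysis of outcome) names the data source for the definitive calculation: "Analysis of baseline data of the first phase aims to describe the mean and SD of the primary and secondary outcome measures".

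Section 7 (Proposed sample size) says that the 100 participants will allow variability in outcome to be assessed for a future power calculation. It adds that the bid at month 18 will include the mean and SD of the primary and secondary outcome from the pilot, without naming a time point. For planning it states that "the likely mean activity of the target population will be approximately 12 hours (with an estimated SD 9"), that "a minimum clinically significant benefit is an increase of 4 hours activity", and that the effect is taken as "a conservative estimate of effect in the 0.3 to 0.4 range". From this it concludes that "a trial with a sample size of approximately 300 cases would have sufficient power to provide a definitive test". No alpha, target power or dropout is attached to the 300.

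Appendix b explains where an SD near 9 comes from. Of the EDIE 2 cases, 122 of 205 were below 30 hours a week, and "they are a more homogeneous sample (Mean 13.96 SD = 8.71"). Table 1 in the same appendix gives structured-activity SDs in samples for which no 30-hour limit is stated: 27.81 for the EDIE ultra high risk sample (N = 288) and 17.54 for the row "ISREP Young people with chronic psychotic disorder and social impairment" (N = 77).

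**The concern.** The target population and inclusion criteria (Sections 3 and 5) admit only people with fewer than 30 hours a week, so every baseline value lies between 0 and 30. The spread of such values is governed largely by the cut-off. After entry nothing limits hours to 30, and the purpose of treatment is to raise them. Some participants can move well up while others stay where they were, which widens the distribution. The protocol nowhere warns that the SD may grow after entry; Appendix b presents the narrow baseline spread as homogeneity of the sample.

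The SD that matters for a two-group comparison of follow-up hours is the follow-up SD. Supplying it is one of the stated purposes of the pilot. If the bid took its SD from baseline, as Section 8 says, the standardised size of a 4-hour gain would be overstated and the definitive trial would be too small.

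**Working it through.** **Inputs.** Minimum benefit 4 h, planning SD 9, effect 0.3 to 0.4, provisional total 300 (Section 7). Entry below 30 h (Sections 3 and 5). SD 8.71 in the subgroup below 30 h and 17.54 in the socially impaired chronic sample (Appendix b). Retention criterion of 90% for the primary outcome (Section 1). *Assumed, because not stated:* two-sided 5%, 1:1 allocation, no covariate adjustment. Results are from the two-sample t test unless marked otherwise.

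**1. How far the entry rule fixes the baseline SD.** A flat spread from 0 to 30 h has SD 30/√12 = 8.66. The EDIE 2 subgroup below 30 h has 8.71, and Section 7 plans on 9. As a further check, a gamma distribution with the full EDIE mean and SD (30.67, 27.81; the shape is an assumption), cut at 30 h, has 61% below the cut, mean 13.7 and SD 8.3. The protocol reports 60%, 13.96 and 8.71. An SD near 9 is what the cut-off produces.

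**2. What a baseline SD would imply.** Normal approximation per arm: n = 2(1.960 + 0.842)²(SD/4)². With SD 9: 2 × 7.849 × 5.0625 = 79.5, so 80 per arm, 160 in total; the t test gives 162. If the trial had 162 cases and the outcome SD were 12 (d = 4/12 = 0.333, 81 per arm), power would be 56%.

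**3. Where the 300 comes from.** It is not 4/9: that is d = 0.44 and needs 162 (80% power) or 216 (90%). The stated effect range does bracket 300:

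| Effect d | SD implied by 4 h (4/d) | Total N, 80% power | Total N, 90% power |
|---|---|---|---|
| 0.30 | 13.3 | 352 | 470 |
| 0.325 | 12.3 | 300 | 400 |
| 0.35 | 11.4 | 260 | 346 |
| 0.40 | 10.0 | 200 | 266 |

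With 10% loss, d = 0.4 at 90% power gives 266/0.9 = 296. Several combinations therefore reach about 300, and the text does not say which was used.

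**4. What 300 delivers for a 4-hour difference** (150 per arm, or 135 per arm after 10% loss):

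| Outcome SD | d = 4/SD | Power, 300 analysed | Power, 270 analysed |
|---|---|---|---|
| 9 | 0.444 | 97% | 95% |
| 10 | 0.400 | 93% | 91% |
| 12 | 0.333 | 82% | 78% |
| 13.3 | 0.300 | 74% | 69% |
| 15 | 0.267 | 63% | 59% |
| 17.54 | 0.228 | 50% | 46% |

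The break-even SD for 80% power follows from 4/[2.802 × √(2/150)] = 12.4 by the normal approximation, or 12.3 by the t test. At SD 17.54, 80% power would need 606 cases.

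**5. When follow-up data exist.** Section 13 recruits the first phase in months 4 to 9. Someone entering in month 9 reaches the 9-month assessment in month 18, the month by which the application is due. Three-month data on the first 40 are planned for the end of year 1 (Appendix a).

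**The case against.** The strongest reply is that Section 7 already promises outcome variability and that the 300 was deliberately conservative. Much of this stands, and it rules out several stronger readings.

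- *A reader might infer a settled plan to use only the baseline SD.* The documents do not support that. Section 7 points the other way, and its statement about the month-18 bid names no time point. What exists is a conflict between two sections, with the worse wording in the analysis section.
- *A reader might infer that 300 was calculated from SD 9, or that 2.7 to 3.6 h (0.3 to 0.4 times 9) shows the inputs to be incoherent.* That follows only if the SD is held at 9. Effects of 0.3 to 0.4 lie below 4/9 = 0.44 and, for 4 h, correspond to SDs of 10 to 13.3. The figure therefore already allows for some widening, and at d = 0.35 or 0.4 its power is 86% or 93%.
- *A reader might apply the SD of 27.81 and conclude that power is about 24%.* That sample includes people at or above 30 h, so its SD is no estimate for this trial. The 17.54 also comes from a different population and is only illustrative.
- *A reader might model follow-up hours from the full EDIE distribution.* With weak baseline to follow-up correlation, such a model makes mean hours rise by 9 to 12 h without treatment. That sits badly with an entry criterion of impairment lasting longer than 6 months, so no power figure is taken from it here.

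Adjusting for baseline hours would also help. With SD 17.54 and an assumed correlation of 0.5 or 0.7, the residual SD is 17.54 × √(1 − r²) = 15.2 or 12.5, and 300 cases have about 63% or 79% power (normal approximation). Section 8 does not name baseline hours as a covariate, though, and the correlation is unknown.

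None of this answers the main point: the wording of Section 8 selects the one time point at which the entry rule restricts the spread.

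**Conclusion.** The concern holds for the source of the SD. Section 8 ties the definitive calculation to baseline data, the entry rule keeps that SD near 9, and Section 7 says something different. Taken literally, Section 8 would lead to about 162 cases for a 4-hour difference at 80% power, which is too few if the outcome SD exceeds 9, as is likely.

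The claim that 300 cases "would have sufficient power to provide a definitive test in a substantive trial" is conditional, not refuted. It holds for 4 h at 80% power only up to an outcome SD of about 12.3 (about 11.7 with 10% loss). At the lower end of the protocol's own effect range it gives 74%, or 69% with 10% loss.

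These figures assume two-sided 5%, equal allocation and an unadjusted comparison. The direction of the bias rests on follow-up hours being uncapped; its size cannot be fixed, because the documents give no outcome SD for entrants below 30 h. The pilot's own target of 100 and its progression criteria are unaffected.

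**What to change.** **Section 8.** Replace baseline data as the source with the follow-up SD of the primary outcome, pooled over the two arms, together with the correlation between baseline and follow-up hours. Use the 9-month data available when the bid is prepared. Name the 3-month data as an interim source, because the last of the first 40 reach 9 months only at month 18. Baseline means and SDs can still be reported as description.

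**Section 7.** Say the same, naming the time point. State the alpha and power assumed for the 300, and show its power for a 4-hour difference across outcome SDs of about 9 to 18, as in the second table above.

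**Cost.** A wording change in two sections and one recalculation, with no new data collection. The provisional figure will look less favourable. The follow-up SD will also rest on few participants: with 40 (38 degrees of freedom, approximate Normality assumed) the 95% limits for the SD are √(38/χ²), or about 0.82 to 1.29 times the estimate. The bid should show that uncertainty.
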